8.4. Fabry Disease Medical History

The data collected on the three CRFs, Fabry Disease Medical History, Fabry Disease Diagnosis, and Fabry Disease Past Treatment, will be listed in a single listing.

Fabry Disease Medical history data by body system and conditions as collected on the CRF form will be tabulated. Number of patients with confirmed condition (answered Yes to the condition in specific) and the percentage based on the total number of patients in consideration will be presented, for overall and by gender.

The analysis will be repeated for the Safety and Efficacy sets.

8.5. Other Medical History

Other medical history will be listed and summarized by descriptive statistics by gender and overall. The analysis will be repeated for the Safety and Efficacy sets.

8.6. Treatment Compliance

Treatment compliance will be assessed by dividing the actual number of bi-weekly infusions, including partial infusion, over the expected number of infusions during the study in 52 weeks.

The compliance will be listed and tabulated for overall and by gender using descriptive statistics for the Safety and Efficacy sets.

8.7. Overall Exposure to Study Treatment

The overall exposure duration (in person-month) and the exposure duration by gender, in person- month will be summarized.

8.8. Infusions

The infusion duration (hours) by visit will be summarized by descriptive statistics by overall.

The number of infusions (partial or full) that a patient received will be summarized by descriptive statistics overall.

Listing of infusion should include whether the infusion was interrupted or not and whether

the complete dose was administered or not (based on data collected at the Drug Administration CRF page).

The analyses will be repeated for the Safety and Efficacy sets.

9. ANALYSIS OF SAFETY ENDPOINTS

Safety analysis will be conducted on the safety analysis set.

9.1. Adverse Events

Adverse events will be coded by the Medical Dictionary for Drug Regulatory Activities (MedDRA) version 15.0 or higher.

9.1.1. Definitions

Pre-treatment AEs include all adverse events collected during the screening and the adverse events occurred before the first pegunigalsidase alfa infusion.

Treatment-emergent adverse event (TEAE) is any AE occurring after the start of the first infusion of pegunigalsidase alfa. In case that date of onset is unknown, the AE will be classified as TEAE and not as pre-treatment AE.

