8.3 Adverse Events

8.3.1 Adverse Events (AE) and Serious Adverse Events (SAE)

An adverse event (AE) is any untoward medical occurrence in a subject participating in a clinical trial. An adverse event can be any unfavorable and unintended sign, symptom or disease temporally associated with the use of the study medication, whether or not considered related to the study medication. AEs will be collected from the start of treatment until 30 days following the final visit dose. Any events occurring prior to treatment will be recorded on the medical history page with the event name and onset date and end date if not continuing. Pre-existing, known clinically significant conditions observed at screening should be recorded as medical history.

This definition also includes accidental injuries, reasons for any change in medication (drug and/or dose) other than planned titration, reasons for admission to a hospital, or reasons for surgical procedures (unless for minor elective surgery for a pre-existing condition). It also includes adverse events commonly observed and adverse events anticipated based on the pharmacological effect of the study medication. Any laboratory abnormality assessed as clinically significant by the Investigator must be recorded as an adverse event.

A treatment emergent adverse event is any adverse event occurring after start of study medication and within the time of residual drug effect, or a pre-treatment adverse event or pre-existing medical condition that worsens in intensity after start of study medication and within the time of residual drug effect.

Adverse events should be recorded as diagnoses, if available. If not, separate sign(s) and symptom(s) are recorded. One diagnosis/symptom should be entered per record.

Note that death is not an event, but the cause of death is. An exception is the event of sudden death of unknown cause. Note that hospitalization is not an event; however, the reason for hospitalization is. Procedures are not events; the reasons for conducting the procedures are. In general, only the reason for conducting the procedure will be captured as an adverse event. However, if deemed necessary by the Investigator, a procedure can be captured along with the reason for conducting the procedure.

An overdose or medication error is not an adverse event unless it is temporally associated with an unfavourable or unintended sign or symptom.

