9.1 Study Visits

9.1.1 Screening Visit S1 (3 Months \pm 7days before Visit 1)

The following procedures will be performed:

- Administration of informed consent
- Assign Screening number
- Medical history, including Fabry disease history
- Demographics
- Alpha-galactosidase activity in plasma and leucocytes
- Historical serum creatinine values
- Vital signs (blood pressure, pulse, temperature and respiration rate)
- Body weight and height
- Physical examination
- Concomitant medications , including review of pain medication and premedication
- Clinical laboratory
 - Hematology
 - Biochemistry
 - Serum Creatinine and Cystatin C
 - Urinalysis by dipstick
 - Spot urine test for proteinuria
 - HbsAg, HCV, HIV
 - Serum pregnancy test (beta HCG)
 - Vit D
 - PT, PTT
 - C3, C4
 - Urine Lyso Gb3 concentration
 - Plasma Lyso Gb3
 - Plasma Gb3
- Electrocardiogram
- Chest X-ray – an X-ray from the previous three months is acceptable
- Cardiac function assessment with echocardiography and stress test
- Review of inclusion and exclusion criteria
- Request subject approval

Schedule the patient for the next visit.

9.1.2 Visits A and B (2 and 1 Month \pm 7 days before Visit 1)

The following procedures will be performed:

- Clinical laboratory
 - Serum Creatinine and Cystatin C
 - Spot urine test for proteinuria
- Concomitant medications including review of pain medication and premedication
- Adverse event assessment

Final enrolment approval will be determined after Visit B.

Schedule the patient for the next visit.

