10.4.1 Adverse Events

Adverse events will be coded to system organ class and preferred term using MedDRA version 15.0 or higher. All adverse events occurring after the initiation of the study treatment (treatment emergent adverse events) will be reported, including events present at baseline that worsened during the study.

Adverse events will be summarized with respect to incidence of adverse events (the number of subjects reporting at least one episode of a specific adverse event), incidence of adverse events by severity within body system, incidence of adverse events by attribution within body system, and incidence of adverse events causing withdrawal and incidence of serious adverse events. Regarding severity and attribution summaries, the most extreme outcome (highest severity and closest to study drug related) will be used for those subjects who experience the same adverse event on more than one occasion.

Written narratives will be provided for all serious, unexpected or other significant adverse events that are judged to be of special interest because of their clinical importance.

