2. INTRODUCTION

The statistical analysis plan (SAP) contains the analysis information in detail on the definition of the analysis populations, derivation of variables, convention of analysis scope, and statistical methodology for the analyses of safety and efficacy parameters of pegunigalsidase alfa (formerly known as PRX-102) administered by intravenous infusion based on the data collected per the protocol PB-102-F30, a phase 3 study sponsored by Protalix, Ltd. In case of disagreement between the SAP and the Clinical Study Protocol, the SAP prevails.

Any deviations from this SAP during the actual data analysis will be documented properly in a change request or a note-to-file document, as well as in the final Clinical Study Report (CSR).

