9.1.2. Pre-Treatment Adverse Events

A table will be presented for the frequency of the pre-treatment adverse events by the MedDRA system organ class and preferred term for overall and by gender.

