9.1.3. Treatment-Emergent Adverse Events (TEAE)

Number and percent of patients with at least one TEAE as well as the number of TEAE in the following categories will be summarized overall and by the subgroups presented in Section 7.4:

- Any TEAE
- Treatment non-related (unlikely, not-related) TEAE
- Treatment related (defined as possibly, probably or definitely related) TEAE
- Mild or moderate TEAE
- Treatment related mild or moderate TEAE
- Severe TEAE

- Treatment related severe TEAE
- Serious TEAEs
- Treatment related serious TEAE
- TEAE leading to withdrawal
- Treatment related TEAE leading to withdrawal
- TEAE leading to death
- Treatment related TEAE related to death.

These tables above will be repeated for the number and percentage of patients with at least one injection site reaction TEAE.

Summary tables will be presented for the frequency of any TEAEs by the MedDRA SOC and PT by overall and by the subgroups presented in Section 7.4; by the MedDRA SOC and PT and severity of TEAE; by MedDRA SOC and PT, and the relationship of TEAEs to study drug.

Summary tables will be presented for the frequency of serious TEAEs by the MedDRA SOC and PT for overall and by gender and by the MedDRA SOC and PT and relationship to study drug.

In the summaries of severity and relationship to study drug, the most extreme outcome (highest severity and closest relationship to study drug) will be used for those subjects who experience the same TEAE (per preferred term) on more than one occasion.

Missing values associated with TEAEs will be treated as missing except for causality, intensity, and outcome of a TEAE, at which occurrence a “worst case” approach will be taken in the analysis. Thus

- If causality is missing, the TEAE will be regarded as related to pegunigalsidase alfa
- If the intensity is missing, the intensity of the AE will be regarded as severe
- If the outcome is missing and the stop date is not provided, the outcome is regarded as “ongoing”.
- If the seriousness is missing, all efforts should be made prior to database lock to make sure that this information is available, if still missing, the worst-case scenario is assumed.

If there were any TEAEs leading to withdrawal or death, these cases will be presented by patient.

Listing of TEAE will include also the TEAE onset and end date and also relative to first pegunigalsidase alfa infusion.

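### SAP 9.1.1 drops the protocol's worsening criterion, so a screening adverse event that worsens after the switch on the same record falls outside the TEAE tables

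*SAP*

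**What the plan says.** The protocol gives the rule twice. In section 8.3.1 a treatment-emergent event is one that starts after study medication, "or a pre-treatment adverse event or pre-existing medical condition that worsens in intensity after start of study medication", in both cases limited to the period of residual drug effect. Section 10.4.1 carries this into the analysis: all events after the start of treatment are reported, "including events present at baseline that worsened during the study".

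SAP 9.1.1 keeps only the first half: "Treatment-emergent adverse event (TEAE) is any AE occurring after the start of the first infusion of pegunigalsidase alfa". Its one exception is an unknown onset date, which counts as treatment-emergent. The same section says: "Pre-treatment AEs include all adverse events collected during the screening", and adds events occurring before the first infusion. SAP 9.1.2 sends that class to its own output: "A table will be presented for the frequency of the pre-treatment adverse events by the MedDRA system organ class and preferred term".

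On precedence, SAP section 2 says: "In case of disagreement between the SAP and the Clinical Study Protocol, the SAP prevails".

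On recording, the protocol is not consistent. Section 8.3.1 says that AEs are collected from the start of treatment and that earlier events go on the medical history page. The section 9 flow chart and section 9.1.2 schedule an AE assessment at screening Visits A and B. The SAP plans a pre-treatment AE table (14.3.1.6) and listing (9.1).

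**The concern.** Safety is the primary objective, and TEAEs are a named safety endpoint. In a switch study, an event already present on agalsidase alfa that becomes more severe on pegunigalsidase alfa is part of the safety question. The protocol's definition includes it, and the SAP's does not.

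Such an event would appear only in the pre-treatment table, which gives frequency by SOC and PT. Its severity after the switch and its relationship to study drug would not be tabulated. For these records the omission can only lower the TEAE count relative to the protocol's definition. Elsewhere the SAP takes the cautious side: an unknown onset becomes a TEAE, and missing causality or intensity takes the worst case.

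**Working it through.** The plan gives no figure to reproduce, because the point concerns a definition. The check applies each rule to three kinds of record.

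| Record | SAP 9.1.1 | Protocol 8.3.1 and 10.4.1 |
|---|---|---|
| Onset in screening, ongoing at first infusion, intensity rises later on the same record | Not a TEAE | TEAE |
| New record opened at the worsening, onset after first infusion | TEAE | TEAE |
| Onset date unknown | TEAE | TEAE |

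The two rules differ only in the first row. That row needs four things together:

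1. The event was entered as an AE and not as medical history.
2. It was ongoing at the first infusion.
3. Its intensity rose afterwards.
4. The site updated the old record and did not open a new one.

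Protocol 8.3.2 asks for start date, stop date and intensity for each event, and for follow-up until the event resolves or is stable. It has no rule for a change in intensity, so condition 4 is possible but not shown.

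No other SAP rule brings the record back. The highest-severity rule in SAP 9.1.3 "will be used for those subjects who experience the same TEAE (per preferred term) on more than one occasion", so it works only on events already classed as TEAEs.

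**Size, for illustration.** Inputs: 22 planned patients (SAP 4.1), all assumed treated; no more than 25% female (SAP section 4); TEAE tables given overall and by gender (SAP 9.1.3 and 7.4). The number of affected patients, k, is not in the documents. The range 1 to 3 is an assumption.

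- Shift in an overall row = k/22, if none of the k patients has another event in that row: 1/22 = 4.5, 2/22 = 9.1 and 3/22 = 13.6 percentage points.
- Female cap: 0.25 × 22 = 5.5, so at most 5 women and at least 17 men. One patient moves a female row by at least 1/5 = 20.0 points and a male row by at most 1/17 = 5.9 points.
- A patient who already has another event in the row changes nothing.

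**The case against.** The strongest reply is the protocol's own recording rule. If events before treatment go on the medical history page, as section 8.3.1 says, a later worsening needs a new AE record with onset after the infusion, and SAP 9.1.1 counts it. This stands for medical-history conditions. It does not dispose of the point, because the same protocol schedules AE assessments at Visits A and B and the SAP expects pre-treatment AEs in a table and a listing.

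A CRF instruction may also require a new record when intensity rises. Protocol 11.2 says that CRF completion is explained to investigators separately, and that material is not in these documents. If the instruction exists and was followed, nothing is lost.

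It can be argued that the SAP is merely silent on worsening, so that the protocol still governs. That fails, because SAP 9.1.1 puts all screening-collected events in the pre-treatment class without qualification, which is a disagreement that the SAP wins.

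Other outputs recover part of the information:

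- Laboratory, physical-examination and ECG shift tables (SAP 9.2 to 9.4) show worsening from baseline.
- Clinically significant laboratory abnormalities must be recorded as AEs (Protocol 8.3.1), and acute kidney injury is an AE judged against the immediately previous creatinine value (Protocol 8.3.3).
- Reasons for hospital admission are AEs (Protocol 8.3.1), and serious or otherwise significant events get narratives (Protocol 10.4.1).
- Reasons for discontinuation are tabulated (SAP 8.1), and pre-treatment AEs are listed (SAP 11.3, listing 9.1).

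These safeguards stand, and they lower the priority. Finally, the percentage shifts are one-patient arithmetic and would fit any single misclassified event. That is also correct, so they are offered only for scale.

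**Conclusion.** SAP 9.1.1 conflicts with the protocol's definition of a treatment-emergent event and should be corrected, at low priority. What can be lost is mainly non-serious clinical worsening, kept on a record opened in screening, in the TEAE count, severity, relatedness and SOC/PT tables. The number of such patients is unknown and may be zero. Each one with no other event in a row moves an overall row by 4.5 points if 22 are treated.

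A reader might infer more, and the documents do not support it:

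- **That all worsening of pre-existing conditions is missed.** Worsening entered as a new AE after the first infusion is counted.
- **That the SAP's definition undercounts TEAEs on balance.** SAP 9.1.1 puts no residual-drug-effect limit on new events and so is broader than the protocol there. The downward direction holds only for the exposed records.
- **That the study's safety conclusion is biased.** Nothing in the documents shows that any such record exists.

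The conclusion rests on reading the SAP's pre-treatment class literally and on the absence, within these documents, of a rule that opens a new record when intensity rises.

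**What to change.** 1. Add the protocol's worsening criterion to SAP 9.1.1, for pre-treatment AEs and pre-existing conditions. Either carry the criterion in full, with its residual-drug-effect limit, or state that the limit is dropped so that worsened events are treated like new-onset events, to which SAP 9.1.1 applies no such limit.
2. Before database lock, review AEs with onset before the first infusion that were ongoing at it. Reclassify as TEAEs those whose intensity rose afterwards. Where the worsening cannot be dated, list the event as worsened with date unknown.
3. Footnote any difference from the interim CSR, because SAP 7.5 says that the final analysis repeats the analyses in that report.
4. Reconcile the medical-history rule in Protocol 8.3.1 with the AE assessments at Visits A and B, and state which convention the sites used.

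A new prospective recording rule would add little: SAP 7.5 puts the interim at about 80% of patients completed or discontinued, or 0.80 × 22 = 17.6, about 18 of the planned 22.

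The cost is a short SAP amendment and a records review in about 22 patients. TEAE counts may rise slightly and differ from the interim CSR. If dated intensity changes were not captured, the onset of worsening cannot be derived. If the review finds no such record, the tables do not change.

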9.1.2. Pre-Treatment Adverse Events

A table will be presented for the frequency of the pre-treatment adverse events by the MedDRA system organ class and preferred term for overall and by gender.

9.1.3. Treatment-Emergent Adverse Events (TEAE)

Number and percent of patients with at least one TEAE as well as the number of TEAE in the following categories will be summarized overall and by the subgroups presented in Section 7.4:

- Any TEAE
- Treatment non-related (unlikely, not-related) TEAE
- Treatment related (defined as possibly, probably or definitely related) TEAE
- Mild or moderate TEAE
- Treatment related mild or moderate TEAE
- Severe TEAE

- Treatment related severe TEAE
- Serious TEAEs
- Treatment related serious TEAE
- TEAE leading to withdrawal
- Treatment related TEAE leading to withdrawal
- TEAE leading to death
- Treatment related TEAE related to death.

These tables above will be repeated for the number and percentage of patients with at least one injection site reaction TEAE.

Summary tables will be presented for the frequency of any TEAEs by the MedDRA SOC and PT by overall and by the subgroups presented in Section 7.4; by the MedDRA SOC and PT and severity of TEAE; by MedDRA SOC and PT, and the relationship of TEAEs to study drug.

Summary tables will be presented for the frequency of serious TEAEs by the MedDRA SOC and PT for overall and by gender and by the MedDRA SOC and PT and relationship to study drug.

In the summaries of severity and relationship to study drug, the most extreme outcome (highest severity and closest relationship to study drug) will be used for those subjects who experience the same TEAE (per preferred term) on more than one occasion.

Missing values associated with TEAEs will be treated as missing except for causality, intensity, and outcome of a TEAE, at which occurrence a “worst case” approach will be taken in the analysis. Thus

- If causality is missing, the TEAE will be regarded as related to pegunigalsidase alfa
- If the intensity is missing, the intensity of the AE will be regarded as severe
- If the outcome is missing and the stop date is not provided, the outcome is regarded as “ongoing”.
- If the seriousness is missing, all efforts should be made prior to database lock to make sure that this information is available, if still missing, the worst-case scenario is assumed.

If there were any TEAEs leading to withdrawal or death, these cases will be presented by patient.

Listing of TEAE will include also the TEAE onset and end date and also relative to first pegunigalsidase alfa infusion.

9.1.4. Time-categories of TEAE

TEAE will be classified by time of occurrence in relationship to the infusion into one of the following 3 categories:

- Occurring during the infusion or within 2 hours after the completion of the infusion
- Occurring between 2 hours after the completion of the infusion and 24 hours after the completion of the infusion
- Occurring at least 24 hours after the completion of the infusion

A summary of TEAE (number and percentage of subjects with TEAE and number of TEAEs) by the MedDRA SOC and PT and by the three time-categories will be presented

The following rules, including imputation convention when there is missing date/time of TEAE onset and/or infusion, will be applied:

Category #1. TEAE occurring during the infusion or within 2 hours after the completion of infusion.

A TEAE will be classified into this category if date and time are available for both the TEAE and the last infusion and the TEAE onset during the infusion or the time from the stop of infusion to time of TEAE onset < 2 hours.

Category #2. TEAE occurring between 2 hours and 24 hours after the completion of infusion.

A TEAE will be classified into this category if

(1) date and time available for both TEAE and the last infusion and the time from the stop of infusion to time of TEAE onset \geq 2 hours but < 24 hours, or

(2) the time of TEAE onset is not available, but the date of TEAE onset is the same day of the last infusion.

Category #3. TEAE occurring at least 24 hours after the completion of infusion.

A TEAE will be classified into this category if

- (1) the date and time available for both TEAE and the last infusion and the time from the stop of infusion to time of TEAE onset \geq 24 hours, or
- (2) the time of TEAE onset is not available, but the onset date is after the date of last infusion, or
- (3) TEAE onset date is incomplete, or
- (4) the date and time of last infusion cannot be determined.

Per the Drug Administration CRF, there are three options: (1). “During the infusion”, (2). “Within 2 hours after the infusion”, and (3). “Up to 24 hours after the infusion” to be selected if the answer is Yes to the question “Did the patient experience an Adverse Event

during or after the infusion?”. The specific adverse event and a date and/or time (not specified, but in the context, the date/time should be the onset date/time of the adverse event) were collected in a text field.

The information will be used to derive the variables necessary to associate with the adverse events entered in the Adverse Events CRF. The record with a selection of the three options but without specific adverse event or date of onset, or vice versa, will not be considered in determination of the time category.

For those adverse events reported on the Drug Administration CRF, matched by the original term of adverse event and onset date/time on the Adverse Events CRF, the time category will be assigned as follows, which overrides the category assigned by the above rules.

Category #1. TEAE occurring during the infusion or within 2 hours after the completion of infusion.

The TEAE will be classified into this category if the selection of the three options is either (1). During the infusion, or (2). Within 2 hours after the infusion.

Category #2. TEAE occurring between 2 hours and 24 hours after the completion of infusion.

The TEAE will be classified into this category if the selection of the three options is (3). Up to 24 hours after the infusion.

Category #3. TEAE occurring at least 24 hours after the completion of infusion.

Not applicable.

